## Table\_1: Statements and Recommendations from the 2019 WSES guidelines for the management of Acute Pancreatitis patients.

1. Severity grading	! ! !	Severe acute pancreatitis is associated with persistent organ failure (cardiovascular, respiratory, and/or renal), and high mortality. Both new classification systems, Revised Atlanta Classification and Determinant-based Classification of Acute Pancreatitis Severity, are similar in establishing the diagnosis and severity of acute pancreatitis (1C). Patients who have persistent organ failure with infected necrosis have the highest risk of death (1C). Patients with organ failures should be admitted to an intensive care unit whenever possible (1C).
2. Imaging	! ! !	On admission, ultrasound (US) should be performed to determine the etiology of acute pancreatitis (biliary) (1C). When doubt exists, computed tomography (CT) provides good evidence of the presence or absence of pancreatitis (1C). All patients with severe acute pancreatitis need to be assessed with contrast-enhanced computed tomography (CE-CT) or magnetic resonance imaging (MRI). Optimal timing for first the CE-CT assessment is 72–96 h after onset of symptoms (1C). Magnetic resonance cholangiopancreatography (MRCP) or endoscopic ultrasound should be considered to screen for occult common bile duct stones in patients with unknown etiology (1C).
3. Diagnostic laboratory parameters	! ! ! !	The cut-off value of serum amylase and lipase is normally defined to be three times the upper limit. C-reactive Protein level $\geq 150$ mg/l at third day can be used as a prognostic factor for severe acute pancreatitis (2A). Hematocrit > 44% represents an independent risk factor of pancreatic necrosis (1B). Urea > 20 mg/dl represents itself as an independent predictor of mortality (2B). Procalcitonin is the most sensitive laboratory test for detection of pancreatic infection, and low serum values appear to be strong negative predictors of infected necrosis (2A). In the absence of gallstones or significant history of alcohol use, serum triglyceride and calcium levels should be measured. Serum triglyceride levels over 11.3 mmol/l (1000 mg/dl) indicate it as the etiology (2C).
4. Diagnostics in idiopathic pancreatitis	!	In idiopathic pancreatitis, biliary etiology should be ruled out with two ultrasound examinations, and if needed MRCP and/or endoscopic ultrasound EUS, to prevent recurrent pancreatitis (2B).

5. Risk scores	!	There are no "gold standard" prognostic score for predicting severe acute pancreatitis. Probably the bedside index of severity of acute pancreatitis (BISAP) score is one of the most accurate and applicable in everyday clinical practice because of the simplicity and the capability to predict severity, death, and organ failure as well as the APACHE-II (very complex) and other scores (1B).
6. Follow-up imaging	!	In severe acute pancreatitis (computed tomography severity index $\geq$ 3), a follow-up CECT scan is indicated 7–10 days from the initial CT scan (1C). Additional CE-CT scans are recommended only if clinical status deteriorates or fails to show continued improvement, or when invasive intervention is considered (1C).
7. Prophylactic antibiotics	!	Recent evidences have shown that prophylactic antibiotics in patients with acute pancreatitis are not associated with a significant decrease in mortality or morbidity. Thus, routine prophylactic antibiotics are no longer recommended for all patients with acute pancreatitis (1A).
8. Infected necrosis and antibiotics	! ! !	Antibiotics are always recommended to treat infected severe acute pancreatitis. However the diagnosis is challenging due to the clinical picture that cannot be distinguished from other infectious complications or from the inflammatory status caused by acute pancreatitis (2A). Serum measurements of procalcitonin (PCT) may be valuable in predicting the risk of developing infected pancreatic necrosis (1B). A CT-guided fine-needle aspiration (FNA) for Gram stain and culture can confirm an infected severe acute pancreatitis and drive antibiotic therapy but is no longer in routine use (1B).
9. Type of antibiotics	!	In patients with infected necrosis, antibiotics known to penetrate pancreatic necrosis should be used (1B). In patients with infected necrosis, the spectrum of empirical antibiotic regimen should include both aerobic and anaerobic Gram-negative and Gram-positive microorganisms. Routine prophylactic administration of antifungal is not recommended in patients with infected acute pancreatitis, although Candida spp. are common in patients with infected pancreatic necrosis and indicate patients with a higher risk of mortality (1B).
10. Monitoring	!	Continuous vital signs monitoring in high dependency care unit is needed if organ dysfunction occurs. Persistent organ dysfunction or organ failure occurrence despite adequate fluid resuscitation is an indication for ICU admission (1C).
11. Fluid resuscitation	!	Early fluid resuscitation is indicated to optimize tissue perfusion targets, without waiting for hemodynamic worsening. Fluid

	administration should be guided by frequent reassessment of the hemodynamic status, since fluid overload is known to have detrimental effects. Isotonic crystalloids are the preferred fluid (1B).
12. Pain control	
 
No evidence or recommendation about any restriction in pain medication is available. Nonsteroidal anti-inflammatory drugs (NSAID) should be avoided in acute kidney injury (AKI). Epidural analgesia should be an alternative or an agonist with intravenous analgesia, in a multimodal approach. Patient-controlled analgesia (PCA) should be integrated with every described strategy. (1C) Dilaudid is preferred over morphine or fentanyl in the nonintubated patient.
 

13. Mechanical ventilation	! Mechanical ventilation must be instituted if oxygen supply, even with high flow nasal oxygen, or continuous positive airway pressure became ineffective in correcting tachypnea and dyspnea. Both non- invasive and invasive techniques can be used, but invasive ventilation is mandatory when bronchial secretions clearance start to be ineffective and/or the patient is tiring of predicted to tire. Lung- protective strategies should be used when invasive ventilation is needed (1C).
14. Increased intra- abdominal pressure	! Limitation of sedation, fluids, and vasoactive drugs to achieve resuscitative goals at lower normal limits is suggested. Deep sedation and paralysis can be necessary to limit intra-abdominal hypertension if all other nonoperative treatments including percutaneous drainage of intraperitoneal fluid are insufficient, before performing surgical abdominal decompression (1B)
15. Pharmacological treatment	! No specific pharmacological treatment except for organ support and nutrition should be given (1B).
16. Enteral nutrition	! Enteral nutrition is recommended to prevent gut failure and infectious complications. Total parenteral nutrition (TPN) should be avoided but partial parenteral nutrition integration should be considered to reach caloric and protein requirements if enteral route is not completely tolerated. Both gastric and jejunal feeding can be delivered safely (1A).
17. Indications for emergent ERCP	
 
! Routine ERCP with acute gallstone pancreatitis is not indicated (grade 1A).
 
! ERCP in patients with acute gallstone pancreatitis and cholangitis is indicated (grade 1B).
 
! ERCP in acute gallstone pancreatitis with common bile duct obstruction is indicated (grade 2B).
 
! ERCP in patients with predicted severe acute gallstone pancreatitis without cholangitis or common bile duct obstruction cannot be
 

	recommended at this time (grade 2B).
18. Indications for percutaneous/endoscopi c drainage of pancreatic collections	
 
Clinical deterioration with signs or strong suspicion of infected necrotizing pancreatitis is an indication to perform intervention (percutaneous/endoscopic drainage)
 

	After 4 weeks after the onset of the disease:
	– On-going organ failure without sign of infected necrosis
	– On-going gastric outlet, biliary, or intestinal
	obstruction due to a large walled off necrotic
	collection – Disconnected duct syndrome
	- Symptomatic or growing pseudocyst
	After 8 weeks after the onset of the disease:
	- On-going pain and/or discomfort (grade 1C)
19. Indications for surgical intervention	! As a continuum in a step-up approach after percutaneous/endoscopic procedure with the same indications
	
 
Abdominal compartment syndrome
 
Acute on-going bleeding when endovascular approach is unsuccessful
 
Bowel ischaemia or acute necrotizing cholecystitis during acute pancreatitis
 
Bowel fistula extending into a peripancreatic collection (Grade 1C)
 

20. Timing of surgery	Postponing surgical interventions for more than 4 weeks after the onset of the disease results in less mortality (2B).
21. Surgical strategy	
 
! In infected pancreatic necrosis, percutaneous drainage as the first line of treatment (step-up approach) delays the surgical treatment to a more favorable time or even results in complete resolution of infection in 25–60% of patients and it is recommended as the first line of treatment (1A).
 
! Minimally invasive surgical strategies, such as transgastric endoscopic necrosectomy or videoassisted retroperitoneal debridement (VARD), result in less postoperative new-onset organ failure but require more interventions (1B).
 

	
 
! Considering mortality, there is insufficient evidence to support open surgical, mini-invasive, or endoscopic approach (1B).
 
! In selected cases with walled-off necrosis and in patients with disconnected pancreatic duct, a single stage surgical transgastric necrosectomy is an option (2C).
 

	! A multidisciplinary group of experts should individualize surgical
	treatment taking local expertise into account (2C)
22. Timing of cholecystectomy	
 
Laparoscopic cholecystectomy during index admission is recommended in mild acute gallstone pancreatitis (1A).
 
When ERCP and sphincterotomy are performed during the index admission, the risk for recurrent pancreatitis is diminished, but same admission cholecystectomy is still advised since there is an increased risk for other biliary complications (1B).
 
In acute gallstone pancreatitis with peripancreatic fluid collections, cholecystectomy should be deferred until fluid collections resolve or stabilize and acute inflammation ceases (2C).
 

23. Open abdomen	
 
! In patients with severe acute pancreatitis unresponsive to conservative management of IAH/ ACS, surgical decompression and use of open abdomen are effective in treating the abdominal compartment syndrome (2C).
 
! We suggest that clinicians should be cautious not to over-resuscitate patients with early SAP and measure intra-abdominal pressure regularly (1C).
 
! We suggest that the open abdomen (OA) be avoided if other strategies can be used to mitigate or treat severe intra-abdominal hypertension in SAP (1C).
 
! We recommend not to utilize the OA after necrosectomy for SAP (unless severe IAH mandates OA as a mandatory procedure) (1C).
 
! We recommend not to debride or undertake early necrosectomy if forced to undertake an early OA due abdominal compartment syndrome or visceral ischemia (1A).
 

24. Open abdomen management and temporary abdominal closure	
 
We recommend the use of negative pressure peritoneal therapy for OA management (1B).
 
We suggest fascial traction be added to NPWT methods (2B).
 
We suggest that further controlled studies be conducted on intra- peritoneal osmotic therapies in SAP (no recommendation)
 

25. Timing of dressing changes	! Open abdomen re-exploration should be conducted no later than 24– 48 h after the index and any subsequent operation, with the duration from the previous operation shortening with increasing degrees of patient non-improvement and hemodynamic instability (1C).
26. Timing for abdominal closure	! Early fascial and/or abdominal definitive closure should be the strategy for management of the open abdomen once any requirements for on-going resuscitation have ceased, the source control has been definitively reached, no concern regarding intestinal viability persist, no further surgical re-exploration is needed, and there are no concerns for abdominal compartment syndrome (1B).

From: Leppäniemi A, Tolonen M, Tarasconi A, Segovia-Lohse H, Gamberini E, Kirkpatrick AW, Ball CG, Parry N, Sartelli M, Wolbrink D, van Goor H, Baiocchi G, Ansaloni L, Biffl W, Coccolini F, Di Saverio S, Kluger Y, Moore E, Catena F. 2019 WSES guidelines for the management of severe acute pancreatitis. World J Emerg Surg. 2019 Jun 13;14:27. doi: 10.1186/s13017-019-0247-0. PMID: 31210778; PMCID: PMC6567462.

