#### Secondary outcomes

- ! Early definitive treatment rate in 2019 vs. 2020: defined as treatment in accordance with the current guidelines (cholecystectomy or ERCP with endoscopic sphincterotomy during the same hospital admission or within 2 weeks of discharge)
- ! 30-day hospital readmission rate in 2019 vs. 2020: defined as hospital readmission within 30days from discharge for recurrent biliary AP while awaiting interval cholecystectomy, or due to post-cholecystectomy complications
- ! Predictive factors of morbidity and mortality in patients with biliary AP

The compliance of surgeons to the most up-to-date international guidelines on biliary AP will be assessed through the analysis of the following attitudes:

! Use of scoring systems for the diagnosis and severity grading of biliary AP

- ! Use of lipase dosage (for the diagnosis) and CRP (for the severity grading) during the diagnostic workup
- ! Use of Ultrasound scan, CT scan, MRCP, and endoscopic Ultrasound scan (EUS) in the correct way and timing
- ! Use of early ERCP and sphincterotomy in case of cholangitis and/or choledocholithiasis
- ! Use of percutaneous and/or endoscopic drainage in case of infected pseudocyst or necrosis
- ! Timing of surgical necrosectomy
- ! Timing of re-laparotomy in case of open abdomen strategies
- ! Use of prophylactic antibiotics/antifungals
- ! Use of somatostatin analogs
- ! Use of early enteral feeding
- ! Use of early definitive treatment strategies, including cholecystectomy and/or ERCP and sphincterotomy

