#### Study design

The MANCTRA-1 study (coMpliAnce with evideNce-based cliniCal guidelines in the managemenT of acute biliaRy pancreAtitis) is an international multicenter, retrospective cohort study to assess the outcomes of patients admitted to hospital with a diagnosis of biliary AP and the compliance of surgeons worldwide to the most up-to-dated international guidelines on biliary AP. The study compares data collected in 2019 (pre-pandemic period) with those of 2020 (Covid-19 pandemic period).

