#### Statistical analysis

The dichotomous variables will be expressed as numbers and percentages, while continuous variables will be expressed as mean and SD, or median and IQR (minimum and maximum values). Student's t test or ANOVA will be used for comparisons of continuous variables between groups. Chi-squared test or Fisher's exact test, as appropriate, will be used for analysis of categorical data. Multilogistic

regression models will be used to investigate clinical attitudes, physical, laboratory, and radiologic variables predictive of morbidity and mortality. A value of P < 0.05 will be considered statistically significant.

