#### Section 6 – Laboratory tests on admission

- ! WBC
- ! Neutrophils
- ! Platelets
- ! INR (International Normalized Ratio)
- ! C-reactive protein
- ! Aspartate aminotransferase AST
- ! Alanine aminotransferase ALT
- ! Total bilirubin
- ! Conjugated bilirubin
- ! Gamma-glutamil-transpeptidase GGT
- ! Serum amylase
- ! Serum lipase
- ! Lactate DeHydrogenase LDH
- ! Procalcitonin PCT
- ! Lactates

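### Six enzymes are collected without the local upper limit of normal, and the pooled predictor models have no step that puts them on a common scale

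*Combined protocol and SAP*

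**What the plan says.** - **Source of the data.** Under Study design, MANCTRA-1 "is an international multicenter, retrospective cohort study". The data collection and data management sections have each centre enter its own records in an online form, with one Local Lead per centre. No central laboratory is mentioned.
- **What is collected.** CRF Section 6, "Laboratory tests on admission", is a list of analyte names, for example "Serum amylase" and "Aspartate aminotransferase AST". Lipase, ALT, GGT and LDH appear in the same way. Neither this section nor any other CRF section has a field for a unit, a reference range or an upper limit of normal. CRF Section 1 identifies the Local Lead but has no hospital or laboratory field.
- **How it is used.** The Statistical analysis section says that "regression models will be used to investigate clinical attitudes, physical, laboratory, and radiologic variables predictive of morbidity and mortality". It states no transformation, standardisation or centre term. The Secondary outcomes list includes "Predictive factors of morbidity and mortality in patients with biliary AP".
- **The reference scale.** Table 1, item 3, reproduces a guideline statement: "The cut-off value of serum amylase and lipase is normally defined to be three times the upper limit". It names amylase and lipase only.
- **The compliance item.** Under Secondary outcomes, compliance is judged partly by "Use of lipase dosage (for the diagnosis) and CRP (for the severity grading) during the diagnostic workup".

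**The concern.** An enzyme value reported by a hospital reflects the patient and also the scale of that hospital's assay. Dividing by the local upper limit removes the second part, and the plan does not collect that limit. When values from many laboratories are pooled in one model, the assay part acts as noise in the predictor and pulls its coefficient toward zero. Fixing units alone would not cure this if limits also differ between assays that use the same unit.

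What is at stake is whether the study can give a fair account of the prognostic value of six candidate predictors. An enzyme could look weaker than it is, or drop out of the model, because of how it was measured.

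**Working it through.** There is no figure in the plan to reproduce on this point. The check has a reading part and an illustrative calculation.

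**1. Reading.** CRF Sections 1 to 14, the data collection and data management sections, and the Statistical analysis section were searched for a unit, upper limit, reference range, central laboratory, standardisation rule or centre term for these enzymes. None was found. A multiple of the local limit therefore cannot be derived from the listed items alone.

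**2. Model.** For each patient, log(raw value) = log(multiple of limit) + log(local limit). Suppose risk depends on the multiple, and the local limit is unrelated to risk. The slope on the raw log value is then approximately the true slope times

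λ = V / (V + U),

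where V is the variance of the log multiple and U the between-laboratory variance of the log limit. Both are assumptions, since the documents give neither.

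**3. Main illustration.** Take V = 1 and limits spread log-uniformly over a k-fold range, so that U = (ln k)²/12.

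| k | (ln k)² | U | λ = 1/(1 + U) |
|---|---|---|---|
| 2 | 0.480 | 0.040 | 0.96 |
| 3 | 1.207 | 0.101 | 0.91 |
| 5 | 2.590 | 0.216 | 0.82 |

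λ comes from a linear approximation. Logistic simulations (400,000 patients, log-odds 0.4 per SD, two assumed baseline risks) gave ratios of 0.95–0.97, 0.89–0.90 and 0.80–0.81, so the approximation is adequate and slightly optimistic at the wider spreads.

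**4. Wider range of assumptions.** λ by SD of the log multiple (rows) and SD of the log limit (columns):

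| | 0.2 | 0.4 | 0.6 |
|---|---|---|---|
| 0.5 | 0.86 | 0.61 | 0.41 |
| 1.0 | 0.96 | 0.86 | 0.74 |
| 1.5 | 0.98 | 0.93 | 0.86 |

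The loss runs from about 2% to 59%. The worst cell is extreme: on the log-uniform scale an SD of 0.6 corresponds to exp(0.6 × √12) ≈ 8-fold variation in limits, combined there with a narrow spread among patients.

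**5. What recovers the slope.** A second logistic simulation used 100 centres of 40 patients, 100 replicates, true slope 0.50, SD of log multiple 1.0 and SD of log limit 0.5. The mean slopes were:

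- values as multiples of the limit: 0.50
- raw values pooled: 0.39, a loss of (0.50 − 0.39)/0.50, about 21%
- raw log values centred within centre: 0.50

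Centring did as well as dividing by the limit because each simulated centre kept one assay throughout and centres did not differ in their true mean enzyme level.

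**The case against.** The strongest case on the other side has four parts.

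- **The three-times sentence is not a study rule.** This stands. It is reproduced guideline text. Patients enter on a clinical and imaging diagnosis, the eligibility criteria set no enzyme threshold, and no endpoint or planned analysis uses one. A reader might infer that the study loses its means of confirming the diagnosis, or that patients will be misplaced around the cut-off. The documents do not support that, because no such confirmation or classification is planned. Nor does the sentence reach AST, ALT, GGT or LDH. For those four the point rests only on possible differences between laboratories.
- **The values can still be put on a common scale.** This also stands. With one Local Lead per centre, records can be linked to a centre, limits can be requested later without reopening a patient record, and values can be centred within centre. A reader might infer that the information is lost. It is not. The plan provides for none of these steps.
- **Numeric entry is inferred.** The laboratory items have no response options, whereas most categorical items do, so numeric entry is the natural reading. The online form is not reproduced, and items such as age and temperature also carry no unit. This is a fair caution, but nothing in the documents shows that a limit is captured anywhere.
- **The size is assumed and probably modest.** This stands. A 2- to 3-fold range costs 4% to 9% of a coefficient. Table 1, item 3, gives prognostic roles to CRP, haematocrit, urea and procalcitonin, and mentions amylase and lipase only for the cut-off.

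**Conclusion.** The omission is real and minor. As written, the plan pools enzyme values across laboratories with nothing to remove differences in assay scale, so the enzyme coefficients are diluted wherever local limits differ. Retaining 96%, 91% or 82% of the true slope is an illustration. It assumes that limits vary log-uniformly, that they are unrelated to risk, that risk follows the multiple of the limit, and that the log enzyme has SD 1.

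A reader might infer that the main results are at risk. They are not. The mortality and morbidity outcomes and their comparison between 2019 and 2020 use no enzyme value, and the lipase compliance item needs only measured or not measured. A reader might also infer that hospital differences will show up as false enzyme effects. That would require local limits to be related to risk, which the documents do not show. The missing centre term is a wider question than this one.

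**What to change.** - Ask each Local Lead once for the centre's upper limit of normal, with its unit, for amylase, lipase, AST, ALT, GGT and LDH. If an assay changed during 2019–2020, ask for both limits and the date of change.
- State in the Statistical analysis section that these six variables enter the models as log(value / local upper limit). Value and limit must be in the same unit, and the ratio is then free of units.
- Where a centre cannot supply a limit, centre its log values within centre. Centred values have a different zero from log multiples, so mark those centres with an indicator or a centre intercept in the model. State that the method assumes one assay and unit per centre and gives up any true difference in mean level between centres.
- If a three-times indicator for amylase and lipase is of interest, report it descriptively. Do not put it in the model beside the log multiple, where it would be a dichotomised copy of the same variable.

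The cost is six limits and units per centre, a second set where an assay changed, and slightly more data preparation. There is no extra work per patient, and the request can still be made after data entry has closed.
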